#### 13.3.2 Expedited Reporting of Serious Adverse Events (SAEs), Serious Adverse Reactions (SARs) and Suspected Unexpected Serious Adverse Reactions (SUSARs)

All SAEs, SARs and SUSARs (see section 13.2 above for definitions) must be recorded on the appropriate CRF (SAE or SAR) and reported to the CTRU **within 24 hours** of the local research team site staff becoming aware of the event (this includes participants who have withdrawn consent for data collection, see section 11.3). Once all resulting queries have been resolved, the original wet-ink CRF will be posted to the CTRU and a copy retained at site.

Please ensure that only one event is reported on each SAE and SAR CRF (details of multiple symptoms should be listed if they relate to the same event).

SAEs, SARs and SUSARs must be reported in an expedited manner (within 24 hours of the research team becoming aware) during the active monitoring period, which is defined as occurring from randomisation (for SAEs) or from the first trial treatment dose (for SARs and SUSARs) up to 7 days after the last dose of trial treatment.

If sites become aware of any SARs or SUSARs occurring after this active monitoring period, these must still be reported in an expedited manner **up until 90 days after the End of Trial**.

# 13.4 Responsibilities

#### **Principal Investigator:**

- 1. Checking for AEs and ARs when participants attend for treatment / follow-up (this may be delegated to an appropriate member of the trial team) and ensuring that AEs and ARs are recorded and reported to the CTRU in line with the requirements of the protocol.
- 2. Checking for SAEs when participants attend for treatment / follow-up (this may be delegated to an appropriate member of the trial team).
- 3. Using medical judgement in assigning seriousness, causality and expectedness using the version of the pharmacovigilance reference copy of the mirtazapine SPC (Medreich Plc; PL number 21880/0053).
- 4. Ensuring that all SAEs (occurring up to 7 days after a participant's last trial treatment dose) and SARs, including SUSARs (occurring up to 90 days after the End of Trial) are recorded and reported to the CTRU within 24 hours of becoming aware of the event and provide further follow-up information as soon as available. Ensuring that SAEs and SARs (including SUSARs) are chased with CTRU if a record of receipt is not received within 2 working days of initial reporting.
- 5. Ensuring that SAEs are reported to local committees in line with local arrangements.

#### Chief Investigator (or nominated individual):

- 1. Clinical oversight of the safety of patients participating in the trial, including an ongoing review of the risk / benefit.
- 2. Using medical judgement in assigning seriousness, causality and expectedness of SAEs where it has not been possible to obtain local medical assessment.
- 3. Review of specific SAEs and SARs in accordance with the trial risk assessment and protocol as detailed in the Trial Monitoring Plan.
- 4. Review of all events assessed as SUSARs in the opinion of the local investigator. In the event of disagreement between local assessment and the Chief Investigator (CI), local assessment will not be downgraded but the CI may add comments prior to reporting to MHRA and REC.

- 5. Assigning Medical Dictionary for Regulatory Activities (MedDRA) or Body System Coding to all SAEs and SARs.
- The Chief Investigator, with input from CTRU and Sponsor, will submit a Development Safety Update Report (DSUR) relating to this trial IMP, to the MHRA and REC annually.

#### CTRU:

- 1. Central data collection and verification of AEs and ARs, SAEs, SARs and SUSARs according to the trial protocol onto a MACRO database.
- 2. Reporting safety information to the independent oversight committee identified for the trial (Trial Steering Committee (TSC)) according to the Trial Monitoring Plan.
- 3. Expedited reporting of SUSARs to the MHRA, REC and Sponsor within required timelines.
- 4. Notifying Investigators of SUSARs that occur within the trial.
- 5. Checking for (annually) and notifying Principal Investigators of updates to the Reference Safety Information for the trial.
- 6. Preparing standard tables and other relevant information for the DSUR in collaboration with the CI.
- 7. Ensuring timely submission of the DSUR to Sponsor and the REC.

#### Sponsor:

- 1. Reporting safety information to the CI, delegate or independent clinical reviewer for the ongoing assessment of the risk / benefit according to the Sponsor's Risk Assessment.
- 2. Ensuring timely submission of the DSUR to the MHRA.

#### Trial Steering Committee (TSC):

- In accordance with the Trial Terms of Reference for the TSC, periodically reviewing unblinded overall safety data to determine patterns and trends of events or identify safety issues which would not be apparent on an individual case basis.
- 2. Unblinded safety data would only be discussed in a closed session without blinded members of the trial team present.

# 14. Participant-reported measures

The various participant-reported measures (all of which will be administered by the researcher) of symptoms, activity, Quality of Life (QoL) and outcomes used in the BETTER-B Feasibility trial have been selected based on a national consensus statement of a National Cancer Research Institute (NCRI) Group on breathlessness , two systematic reviews of measures of breathlessness , and a study estimating the size of a clinically important difference .

Most of these measures are brief scales, with a total of 70 participant-reported questions (at baseline), which overall (time for the questions and observation) take around 30-45 minutes to complete. This has been found acceptable in other studies . As part of this BETTER-B Feasibility trial we will assess which scales are suitable for a future large-scale trial based on missing data, patient acceptability and time to complete, so that the questions can be kept to a minimum in the future trial.

The participant-reported measures used in the BETTER-B Feasibility trial are:

- Numerical Rating Scale (NRS) for breathlessness: this assesses the severity of breathlessness in the previous 24 hours on a 0-10 numerical rating scale, for average, and worst . It will be administered to participants at baseline and at the assessment calls/visits for days 7, 14, 21 and 28.
- Modified Medical Research Council (mMRC) dyspnoea scale: this assesses the overall level of breathlessness and will be administered to participants at assessment visits for days 14 and 28.
- Chronic Respiratory Disease Questionnaire (CRQ):xxxiii this is a 20 item widely validated health-related quality of life questionnaire. Experiences are rated on 7-point scale ranging 1 (maximum impairment) to 7 (no impairment)  This will be administered to participants at baseline and at the assessment visits for days 14 and 28 .
- EQ-5D-5L: this assesses mobility, self-care, usual activities, pain/discomfort, anxiety/depression according to three levels of severity (1=no problems; 2=some or moderate problems; 3=extreme problems), plus a Visual Analogue Scale (VAS) of current health-related quality of life, scored 0-100. This will be administered to participants at baseline and at the assessment visit for days 28.
- Integrated Palliative care Outcome Scale (IPOS):xxxiv this is a brief measure for advanced disease widely validated in cancer and non-cancer. Each item is rated 0 (no

xxxiii Copyright University Hospitals of Leicester NHS Trust.

xxxiv Permission to use obtained from the Cicely Saunders Institute.

problem) to 4 (overwhelming problem). This will be administered to participants at baseline and at the assessment visits for days 14 and 28 .

- Generalized Self-Efficacy Scale (GSES): this assesses optimistic self-beliefs to cope with a variety of difficult demands in life. This will be administered to participants at baseline and at the assessment visit for days 28.
- Hospital Anxiety and Depression Scale (HADS):xxxv this is a widely used and validated scale used to assess anxiety and depression and has validity in older people to assess change, which will be administered to participants at baseline and at the assessment visits for days 14 and 28 .
- Client Services Receipt Inventory (CSRI): is an assessment tool where patients reported the health, voluntary and social care services received over the last four weeks at baseline and at the assessment visit for day 28.

# 15. Economic Evaluation

The economic evaluation component of this trial aims to test the feasibility of collecting cost data, with modified CSRI, and quality of life data, with EQ-5D-5L. We will develop the tailored CSRI questionnaire, considering patient understanding and care settings. It will be ideal to collect cost data by formal health care, social care and informer care separately. We will identify difficulties answering CSRI questions, if any, by checking item response rate and reading free text answers to open-ended questions.

We will calculate the summary statistics of formal and informal care costs (and social care costs, if possible) for the last four weeks at baseline and at the assessment visit for day 28.

Finally we will examine the possibility of assessing the cost-effectiveness using outcome measurements (average breathlessness severity measured by NRS for breathlessness, breathlessness mastery measured by CRQ and IPOS and Quality Adjusted Life Years (QALYs) derived from using EQ-5D-5L) at 4 weeks. We will explore if it is possible to produce a cost-effectiveness plane with the results from the cost-effectiveness analysis.

<sup>xxxv HADS copyright © R.P. Snaith and A.S. Zigmond, 1983, 1992, 1994.Record form items originally published in Acta Psychiatrica Scandinavica 67, 361–70, copyright © Munksgaard International Publishers Ltd, Copenhagen, 1983.This edition first published in 1994 by nferNelson Publishing Company Ltd (now GLAssessment Ltd),[name] GL Assessment Ltd is part of the Granada Learning Group.

# 16. Endpoints

# 16.1 Primary Endpoint

The primary endpoint is the number of patients recruited across 3 hospitals over a 12-month period. This has been chosen to determine whether a larger scale trial of the same design is feasible, when expanded to additional centres . The decision to proceed to a future without further amendments will be based on the ability to recruit an average of 5 patients per month within a 12-month period (e.g. approximately 60 patients).

# 16.2 Secondary Endpoints

#### 16.2.1 Feasibility

Other outcome measures of feasibility will be assessed to determine whether the design of the future large-scale trial may need to be adapted to improve recruitment or reduce attrition. Physical activity and toxicity outcomes will be used to inform the design of the future trial, however they will not be used to inform the decision as to whether or not to proceed to a future large-scale trial. These are:

- Number of patients screened for eligibility and reasons for non-eligibility
- Proportion of eligible patients randomised and reasons for non-randomisation
- Proportion of participants for which blinding is maintained
- Proportion of research assessors for which blinding is maintained
- Proportion of participants remaining on study for 28 days
- Proportion of, and reasons for, participants with missing data for trial outcomes
- Proportion of participants who would be eligible for dose escalation at 28 days
- Treatment compliance over the period

Feasibility outcome measures relating to recruitment will be assessed by the use of screening logs completed at each site.

Blinding will be assessed using the Bang Blinding index .

Missing data and study compliance will be assessed based on completed and received CRFs, summarised for each trial outcome measure .

Eligibility for dose escalation will be assessed based on breathlessness intensity at day 28 and tolerability of treatment.

#### 16.2.2 Activity

- **Key Activity endpoint:** severity of breathlessness at the assessment visit for day 28 as assessed by the NRS ("at worst" severity of breathlessness over the last 24 hours).
- Severity of breathlessness at the assessment visits/calls for days 7, 14 and 21, as assessed by NRS (average and "at worst" severity of breathlessness as assessed over the last 24 hours).
- Lower extremity functioning as assessed by the Short Physical Performance Battery (SPPB)  at the assessment visit for day 28.
- Opioid medication: at the assessment visits/calls for days 7, 14, 21 and 28.

#### 16.2.3 Safety and Toxicity

- Adverse events, using the Common Terminology Criteria for Adverse Events (CTCAE) categorisation (v4)  as reported at the assessment visits/calls for days 7, 14, 21 and 28.
- Safety will be reported based on the occurrence of SAEs, SARs and SUSARs.
- Australia-modified Karnofsky Performance Status (AKPS) and modified Medical Research Council (mMRC) dyspnoea scale at the assessment visits for days 14 and 28.

#### 16.2.4 Symptoms and Quality of Life

- Coping self-belief assessment as assessed by the General Self-Efficacy Scale (GSES) at the assessment visit for day 28.
- Mobility, self-care, usual activities, pain/discomfort and anxiety/depression as assessed by EQ-5D-5L at the assessment visit for day 28.
- Palliative symptoms as assessed by the Integrated Palliative care Outcome Scale (IPOS) at the assessment visits for days 14 and 28.
- Anxiety and depression as assessed by the Hospital Anxiety and Depression Scale (HADS) at the assessment visits for days 14 and 28.
- QoL as assessed by Chronic Respiratory Questionnaire (CRQ) at the assessment visits for days 14 and 28.

# 17. Statistical Considerations

#### Sample size and planned recruitment rates

As the trial is designed to assess the feasibility of conducting a future definitive large-scale trial, a formal power calculation is not considered appropriate as effectiveness is not being formally evaluated.

The future large-scale trial would be designed to detect a minimum clinically important effect size of 0.5 in NRS (or a 1 point change) . With 90% power testing at the 5% two-sided significance level, approximately 90 participants per arm would be required. This sample size calculation will be revisited based on the observed variability of the primary outcome in this feasibility trial. It is expected that attrition rates will be approximately 20%, however this will be assessed within this feasibility trial. Assuming a 20% attrition rate, the future trial would require approximately 230 participants in total.

Feasibility of recruitment to a future large-scale trial of the same design will be concluded if the trial is able to recruit an average of 5 patients per month over a 12-month period, equivalent to approximately 60 patients, based on 3 recruiting sites. This equates to 1-2 patients per month, per site. The sites taking part in the feasibility trial are representative of those sites which would be involved in the future larger trial. Assuming 11 sites open to recruitment in the future trial, recruiting 1-2 patients per month each, this would mean a 230-participant trial would be expected to recruit in approximately 18 months to allow for the setup and initiation of all sites.

For this feasibility trial we plan to recruit approximately 60 patients in total (i.e. 30 patients to each treatment arm) from 3 sites in the UK over a 12-month period. Guidance on pilot study design by Browne et al  state that at least 30 patients should be included to estimate a parameter for future sample size calculation . In order to estimate the expected variability of the future large-scale trial's primary outcome measure of breathlessness ("at worst") at day 28 in the mirtazapine arm, 30 participants are required. As the future trial will be randomised, this equates to a total of 60 participants required, with 1:1 randomisation.

# 18. Statistical Analysis

# 18.1 General Considerations

Statistical analysis of the main feasibility trial is the responsibility of the CTRU Statisticians. The analysis plan outlined in this section gives a brief description of the statistical analyses which will be carried out at the end of recruitment and trial follow-up. A final, more detailed, statistical analysis plan will be written before any analysis is undertaken. Given that this is a feasibility trial, the analysis will require descriptive statistics rather than any formal hypothesis testing.

Baseline characteristics of patients will be summarised.

Qualitative and Health Economics analyses will be the responsibility of the qualitative researcher and health economist respectively.

### 18.2 Analysis populations

The primary endpoint analysis will be based on the population of participants randomised within the 12-month recruitment period.

Endpoints which relate to data collected prior to randomisation will be analysed using all patients approached for entry to the study.

Analyses of safety data will be carried out on the safety population, defined as those participants receiving at least one dose of trial treatment, and will summarise participants according to the treatment actually received.

The remaining analysis will be carried out on the intention-to-treat (ITT) population defined as all participants randomised to the trial, regardless of adherence to the protocol, withdrawal of consent or losses to follow-up. Participants will be included within the treatment arm to which they were randomised.

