# 3. Trial Schema

#### **Identification of Potential Participants**

By recruiting trial sites, or by PICs; alternatively patients may contact a recruiting trial site directly (trial publicity). Potential participants include those who have been diagnosed with cancer, COPD/ILD or chronic heart failure, with a prognosis of ≥2months and severe breathlessness (i.e. anticipated mMRC score of Grade 3 or 4)

Is the patient potentially eligible, based on preliminary available information? (e.g. no existing antidepressant use, etc.)

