# 12.2 Screening Data

All patients who have significant breathlessnessxv but do not go on to be randomised must be included on the monthly Screening Logxvi. Anonymised information for these patients will be collected including:

- Disease area diagnosis (e.g. cancer, heart or liver disease)
- Identification setting (community services, outpatient clinic, inpatient clinic)
- Method of initial approach
- Date screened
- Approached / Not approached for the trial
- Reason for non-randomisation:
  - o not eligible for trial participation, or
  - o eligible but declined and reason for this (where appropriate), or
  - o other reason for non-randomisation

This information will be collected from trial sites on a monthly basis. Documented reasons for ineligibility or declining participation will be closely monitored by the CTRU. Screening data forms a crucial endpoint of this feasibility study therefore it is essential that this information is completed and returned to CTRU as outlined.

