# 18.5 Secondary Endpoint Analysis

#### 18.5.1 Feasibility

The number of approaches to patients and randomisations in total throughout the randomisation period and per month will be summarised overall and by recruitment setting and diagnosis. The proportion of screened patients who are eligible for randomisation will be presented with corresponding 95% confidence intervals. Reasons for non-eligibility will be summarised. The proportion of eligible patients who are randomised will be presented with corresponding 95% confidence intervals. Reasons for non-eligibility be summarised.

The proportion of participants for whom blinding is maintained will be summarised overall and by treatment arm, and also by recruitment setting and diagnosis, with corresponding 95% confidence intervals. The proportion of participants who became unblinded and the reasons for unblinding will also be presented. The blinding index for each arm will be calculated using the bang blinding method along with 95% confidence interval. The blinding index calculates the difference between the proportion of correct and incorrect "guesses". The blinding index takes values between -1 and 1.

The proportion of participants who remain on study for 28 days, will be summarised overall and by treatment arm, and also by recruitment setting and diagnosis, with corresponding 95% confidence intervals. The proportion of participants who stop treatment early and the reasons for stopping treatment will be presented.

The proportion of participants who would be eligible for dose escalation at 28 days, will be summarised overall and by treatment arm, and also by recruitment setting and diagnosis, with corresponding 95% confidence intervals. Those participants who would have not been eligible for dose escalation will be summarised along with the reason why they were not eligible for dose escalation.

The proportion of participants with missing data for each trial outcome separately will be summarised overall and by arm, at each time point of assessment. Where available, reasons for missing data will be provided.

Treatment compliance will be summarised by the proportion of participants with dose reductions or omissions and total number of missed doses, by treatment arm. Reasons for dose reductions or omissions will also be presented.

Qualitative data will be analysed by the qualitative researcher. A separate analysis plan will be written outlining the proposed analysis.

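### Section 18.2 restricts pre-randomisation endpoints to patients approached, but 16.2.1 and 18.5.1 define those endpoints on patients screened

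*Protocol*

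**What the plan says.** Section 18.2 fixes one population for everything measured before randomisation: "Endpoints which relate to data collected prior to randomisation will be analysed using all patients approached for entry to the study".

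The endpoints it governs are worded on a different group. Section 16.2.1 lists "Number of patients screened for eligibility and reasons for non-eligibility", and section 18.5.1 says: "The proportion of screened patients who are eligible for randomisation will be presented with corresponding 95% confidence intervals". Section 16.2.1 also names the data source: "Feasibility outcome measures relating to recruitment will be assessed by the use of screening logs completed at each site".

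Section 12.2 requires the log to cover every significantly breathless patient who is not randomised, and one of its fields is "Approached / Not approached for the trial". The trial schema (section 3) contains an early check: "Is the patient potentially eligible, based on preliminary available information? (e.g. no existing antidepressant use, etc".

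A second endpoint in 16.2.1 is "Proportion of eligible patients randomised and reasons for non-randomisation". In 18.5.1, the sentence that presents this proportion is followed by "Reasons for non-eligibility be summarised", a repeat of the summary already promised for the screened-to-eligible step.

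**The concern.** A population limited to those approached cannot yield a number screened, and it changes the denominator of the eligible proportion. The patients at risk of being left out are those set aside on preliminary information, such as existing antidepressant use, which is also the first exclusion criterion in 8.2. Their reasons for ineligibility would leave the table with them.

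Section 12.2 describes the screening data as crucial to this feasibility study. Section 16.2.1 says these measures will help decide whether the design of the large trial must be adapted to improve recruitment. Two analysts could follow two sections of the same protocol and report different eligible fractions.

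The repeated phrase in 18.5.1 adds a smaller fault. Eligible patients have no reasons for non-eligibility, so the analysis section omits the summary that its own endpoint asks for.

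**Working it through.** **Are approached and screened the same group in this protocol?**

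- Section 12.2 gives approach its own yes/no field within the log, so a logged patient may be not approached.
- Section 18.5.1 counts approaches to patients in one sentence and uses screened patients as a denominator in another.
- Section 18.2 neither equates the terms nor exempts the screened-based endpoints.

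Approached is therefore a subset of screened, and the two rules give different results whenever anyone is screened but not approached.

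**What happens to the eligible proportion if 18.2 is followed?**

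The protocol gives no expected numbers screened, approached or eligible, so there is no planned figure to reproduce. Let:

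- S = number screened, E = number eligible, p = E/S
- u = share of screened patients not approached
- q = share of those not approached who are eligible

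Proportion on the screened denominator: p = E/S.

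Proportion on the approached denominator: (E - q·u·S) / (S·(1 - u)) = (p - q·u)/(1 - u).

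With q = 0 this is p/(1 - u). The factor is 1.11 at u = 10%, 1.43 at 30% and 2.0 at 50%. In general the approached figure is higher than p when q < p, equal when q = p, and lower when q > p.

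Illustration with assumed S = 300 and E = 90, so the screened-based proportion is 90/300 = 30.0% (Wilson 95% CI 25.1 to 35.4). The approached-based proportion is then:

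| u | q = 0 | q = 10% | q = 30% | q = 50% |
|---|---|---|---|---|
| 10% | 33.3% | 32.2% | 30.0% | 27.8% |
| 30% | 42.9% | 38.6% | 30.0% | 21.4% |
| 50% | 60.0% | 50.0% | 30.0% | 10.0% |

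Example for u = 30%, q = 0: 90 of 300 are not approached and none of them is eligible, giving 90/210 = 42.9% (95% CI 36.4 to 49.6). Example for u = 30%, q = 50%: 45 of the 90 not approached are eligible, giving (90 - 45)/210 = 21.4%.

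**What happens to the proportion of eligible patients randomised?**

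Restricting to approached patients removes any eligible patient who was never approached from the denominator, while the numerator stays the same. Take 60 randomised (the planned total) and the assumed 90 eligible: 60/90 = 66.7%. With u = 30% and q = 10%, 9 eligible patients were not approached, so the figure becomes 60/81 = 74.1%. With q = 0 nothing changes.

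**The case against.** The strongest reply is that the specific wording should prevail over the general sentence. Section 18.5.1 names screened patients as one denominator and eligible patients as the other, and it promises the reasons for non-eligibility. Section 16.2.1 draws on the full screening log, and 12.2 requires the unapproached to be logged with a reason. On that reading nobody is lost. This stands as far as it goes: the bias arises only if 18.2 overrides 18.5.1. It does not remove the conflict, because 18.2 is the section that defines analysis populations and nothing says it yields.

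A reader might infer that the trial will overstate eligibility. The documents do not support that as a fact. Not approached is a separate log field from the reason for non-randomisation, and those reasons include a general other category, so some unapproached patients may be eligible. The bias can vanish or reverse, as the table shows. Section 9.3 also places some eligibility assessment after patients have assented, and the schema text shows the preliminary question without the steps after it. How many patients are set aside before approach is unknown.

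A reader might also infer that the decision to proceed is at risk. It is not. That decision rests on recruiting an average of 5 patients per month over 12 months, and the projection for the large trial in section 17 uses sites and monthly recruitment rather than a screening yield. The sertraline trial's exclusions in 5.3 are background, and no endpoint compares the two drugs' eligible fractions.

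Finally, 18.1 defers detail to a later analysis plan. That would answer an omission. Here the protocol states a rule, and the rule contradicts its own endpoints.

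**Conclusion.** The inconsistency is certain on the text: 18.2 assigns the pre-randomisation endpoints to a group from which the number screened cannot be obtained, against 16.2.1 and 18.5.1. Its effect on the eligible proportion is conditional. It requires 18.2 to be followed, and its size and direction depend on u and q, neither of which the protocol gives. If all unapproached patients were ineligible, the inflation is 1/(1-u), or 1.11 to 2.0 times over an assumed 10% to 50% not approached. If they were as often eligible as the rest, there is none, and if more often, the proportion is understated.

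The primary endpoint and the recruitment criterion are untouched. What is affected is a descriptive secondary result that the protocol itself treats as important for designing the next trial. The misplaced phrase in 18.5.1 is a drafting slip: the endpoint is stated correctly in 16.2.1 and the reasons are collected under 12.2.

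**What to change.** 1. In 18.2, replace the approached population by all screened patients, meaning everyone on the screening logs plus everyone randomised. Apply it to number screened, proportion eligible and reasons for ineligibility, each reported by approached or not approached.
2. Keep eligible patients as the denominator for the proportion randomised, as 18.5.1 already has it, and state that patients who are eligible but not approached count in it.
3. In 18.5.1, change the second mention of reasons for non-eligibility to reasons for non-randomisation, to match 16.2.1.

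The cost is a few sentences. The trial sites' logs already record approach status and the reason for non-randomisation. The log's other-reason category does not by itself show whether a patient was eligible, so patients in it whose eligibility is unknown should be shown as a separate count.
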